2.2 Aims

Healthcare technology assessment is the multidisciplinary evaluation of medical technologies with regard to **feasibility, safety, efficacy**, indications for use, cost, and cost-effectiveness. A complete assessment should explore the scientific, ethical, economic, and social reasons for adopting a technology and it may influence the quality of service and distribution of resources.

In this multicenter study, we aim to assess the first 3 important criteria.

Aim 1 – To determine the **feasibility** of using a wireless system immediately after delivery and for the first 2h of age, while in the obstetrical center under unsupervised parents' care. The following outcomes will be measured for both wired and wireless systems:

- a. Percentage of time for which HR, RR, SpO₂ and T_{skin} data are displayed.
- b. Occurrence of gaps in signal detection/recordings (% and length).
- c. Causes of the gaps in signal detection/recordings.
- d. Descriptive analysis of user surveys and their satisfaction with the wireless system.

Aim 2 - To investigate the **safety** of using this wireless system immediately after delivery and for the first 2h of age. The following outcomes will be measured for both wired and wireless systems:

- a. Skin score to be determined by a blinded dermatologist using de-identified pictures of the skin after removal of the sensors of each system.
- b. Pain scale to assess any discomfort or pain during the removal of the sensors.
- c. Clinically significant events detected by the wired system (HR < 100 bpm or SpO₂ < 80%) but missed by the wireless system.

Aim 3 – To assess the **accuracy** of this wireless system in measuring HR, RR, SpO₂ and T_{skin} signals compared with the “standard of care” wired system. The following outcomes will be computed:

- a. Correlation coefficient
- b. Slope
- c. Variance accounted for
- d. Bias

Further subgroup analyses will be conducted to assess for systematic differences in feasibility, safety, and accuracy of the wireless system between the following:

- High vs. Low and Middle income countries
- Female vs. Male subjects
- Term vs. Preterm (born < 37 weeks gestational age) infants
- C-section vs. Vaginal delivery

- Skin pigmentation

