- Skin Pigment: Previous research has highlighted the challenges of some pulse oximeters in providing accurate readings for skin with darker pigmentation and as a result has emphasized the need to investigate the performance of pulse oximeters for different skin tones^{38,39}. The infant's skin color will be recorded using the adapted Munsell System Soil Color Chart (2009 Revision, Munsell Color, Grand Rapids, Michigan), Hue7.5YR to investigate impact of skin pigmentation on pulse oximetry accuracy. This scale has previously been used in research on neonates⁴⁰.
- *Pain Assessment*: As well, neonatal pain will be assessed throughout the sensor removal process. The pain scale (NIPS) will be completed by the study team member at the time of sensor removal and entered into REDCAP.
 - Neonatal Infant Pain Scale (NIPS)³⁶ : At the time of device removal, the researcher will complete the NIPS to ensure removal of adhesive does not cause significant discomfort to the patient. The scale consists of 6 items. Scores range from 0 to 7, with scores greater than 3 indicating presence of pain. This scale has been widely validated for the assessment of acute pain in neonates. This scale will be included in the Data Collection Form.
- *Surveys*: In order to assess feasibility on the use of wireless sensors to monitor babies after birth, a survey will be conducted to get the opinions of parents and Health Care Professionals involved in the care of the baby and mother. The survey will be presented in hard copy form as well as through REDCAP.
 - Parent Survey: Parents of the participating infant will be asked to complete a short survey to after the sensors of both systems are removed. The survey will be coded with the study code assigned to the participating infant, no personal health information or personal information will be asked of the parent for the completion of the survey. (See Appendix 2).
 - Health Care Professional Survey: HCPs involved in the care of the infant and mother after birth will be asked to complete a short survey after the sensors of both systems are removed in order to assess how the HCPs felt about the wireless skin sensors as compared to their experience of the standard of care wired monitoring system. (See Appendix 2).

REDCAP

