Clinical data, images, information as described in the Data Collection Form (Appendix 1) and Survey (Appendix 2) responses will be entered into a REDCAP database hosted at the RI-MUHC through the CORD platform. A service agreement has been entered into with CORD and the Principal Investigator for the REDCAP database set up and support for the study's data management. Each participating site will be provided access to the study REDCAP database at the RI-MUHC and be responsible for entering their site's

data into REDCAP. Participating sites will be expected to sign a site user agreement before permitting access to REDCAP. The HCP and parents will be provided a link to the survey in REDCAP or a hard copy depending on their preference and/or the preference of each participating site. The sites will be asked to send their a copy of each completed Data Collection Form and a hard copy of the survey in order to query and ensure compliance and consistency in the conduct of data collection and data entry on a monthly basis. No site will be able to access another site's individual site data and will only have access to REDCAP for their site. The de-identified study database will only be accessible to the lead site and all analysis of the study data collected in REDCAP will be done by RI-MUHC study team members. Results will be shared with the participating sites on an ongoing basis for training purposes as well as to support the drafting and submission of manuscripts, abstracts, and presentations as the study progresses.

BIODASH

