As part of the Smart Hospital Project, this Study and potential future research studies to improve the quality, accuracy and efficiency of monitoring neonates admitted in the NICU, the participants' information may be shared with academic or commercial third parties and used by the research team in other related research studies. Any use of the RI-MUHC and participating site's data in future research studies will be approved by competent research ethics boards and no data that could identify the participant will be shared. Participants at all participating sites will be asked to consent to the sharing of their data collected during this study as well as for use in future research in the field of neonatal care and monitoring. The participants' data will be kept confidential to the extent required by applicable laws. The research agreements with the participating sites will include all the terms and conditions required for the use and sharing of the data from participating sites.

4 Statistical Analysis and Rationale

Sample size: The proposed sample size is 100 newborns/site (n=600) to be recruited over 2 years from start of the Study at each site.

The expected mean and standard deviation are required for estimating the mean effects which is used to determine the absolute precision. In our first study with wireless sensors (see preliminary data) or *phase 1a*, 100 patient recordings (25 infants x 4 days) were expected but only 96 were obtained, resulting in a 4% drop-out rate. Further, the average coverage across wired HR signals was $98.7 \pm 2.2\%$, while that of wireless signals was $85.3 \pm 14.3\%$. Assuming a two-sided significance of 0.05, a study power of 0.9, and accounting for the drop-out rate of 0.04 in all calculations, we can expect an effect size of 2.7% in HR coverage, with the selected sample size of 600 infants. In the case of SpO₂ monitoring, the average coverage was $93.9 \pm 6.3\%$ in the wired system and $66.5 \pm 20.8\%$ in the wireless. In our proposed study, we

can thus expect a difference of 3.46% in SpO₂ coverage. For the statistical measures used to assess the agreement between the wired and wireless vital signals, the average findings from *phase 1a* are reported in the Table. Using the same parameters listed previously, the margin of error expected for each statistical measure in the proposed study can be found.

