5.1 Recruitment plan and consent of participants

At each participating site, the local research team will meet with the obstetrical team to identify potential candidates for participation in the study. Following that, eligible patients will be approached early in their labor stage to assess willingness to participate. If consent is obtained, the research team members will follow the course of the delivery. At the time of birth, infants will only be included if ≥ 35 weeks of gestational age and clinically stable as determined by the attending pediatrician. Written consent will be obtained from parents prior to enrollment. The study protocol has been designed respecting the special moment around birth. Hence, parents will be approached and receive explanation about the study design before delivery and given ample time to make an informed decision. Families will be able to withdraw from the Study at any time. However, any data collected up to date of withdrawal will not be destroyed in order to maintain the integrity of the study design. No further data will be collected once a participant is withdrawn from the Study.

As the study is not a randomized clinical trial a Data Safety and Monitoring Committee (DSMC) will not be established. However, interim evaluations for safety will be done by the lead site after 200 and 400 patients have been studied to review data related to safety, including skin lesion, pain scores, and HCPs survey responses. Any adverse event or evidence of discomfort during monitoring, including placement and removal of sensors (expected to be negligible) will be recorded and reported to the local investigator and the Principal Investigator at the lead site.

Recruitment material in the form of posters and brochures will be provided to all the sites explaining the Study and how to get additional information if interested.

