1. What are your main concerns with the implementation of a new wireless technology in the Delivery Room? (Mark any that apply - multiple choices permitted)

Chest Sensor

- a. Accuracy (good and reliable data)
- b. Challenges using sensors
- c. Safety of stickers used to apply sensors
- d. Size of the sensors
- e. Weight of the sensor
- f. Battery life of wireless sensors
- g. No concerns
- h. Other (please specify):

Limb Sensor

- a. Accuracy (good and reliable data)
- b. Challenges using sensors
- c. Safety of stickers used to apply sensors
- d. Size of the sensors
- e. Weight of the sensor
- f. Battery life of wireless sensors
- g. No concerns
- h. Other (please specify):

1. What do you think might be the impact of a wireless system on bonding between parents and their babies?

- a. Strongly negative
- b. Negative
- c. Neutral
- d. Positive
- e. Strongly positive

1. What do you think might be the impact of a wireless system on your baby's hospital experience? (Mark any that apply - multiple choices permitted)

- a. Easier Kangaroo care (KC) initiation
- b. Increase the amount of time on KC
- c. Reduce discomfort

- d. Decrease pain
- e. Better sleep
- f. Newborn safety
- g. None
- h. Other (please specify):

1. Any additional comment (s):

DO NOT COPY

HEALTH CARE PROFESSIONAL'S SURVEY

Subject ID:

() Neonatologist () Neonatal Fellow () Pediatric Resident

() Registered Nurse () Neonatal Nurse Practitioner

() Respiratory Therapist

() Other: _____

Years of experience: () < 2 years () 2-5 years () 6-10 years () > 10 years

Section 1: Current State of Monitoring with Wires and Cables

1. How satisfied are you with the use of monitoring system with wires and cables immediately after birth and up to 2h of age in the DR?

- a. Very dissatisfied
- b. Dissatisfied
- c. Neutral
- d. Satisfied
- e. Very satisfied

2. What are your main concerns with the monitoring system with wires and cables? (Mark any that apply - multiple choices permitted)

- a. Inaccurate readings
- b. False alarms
- c. Issues associated with adhesion of the sensors (heat generation or pressure and skin irritation)
- d. Too many sensors applied to the skin
- e. Too many wires around the baby
- f. Difficult to handle the baby because of the multiple wires and cables
- g. The sensors, wires and cables are intimidating to the parents
- h. I do not have concerns
- i. Others (please specify): _____

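### The staff survey is triggered by each study infant but carries no respondent code and no once-per-person rule, so frequent attenders can be over-weighted in the staff percentages, and this cannot be undone at person level

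*Combined protocol and SAP*

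**What the plan says.** Section 3.3.4 (Surveys) sets the trigger for the staff request: "HCPs involved in the care of the infant and mother after birth will be asked to complete a short survey after the sensors" (wired and wireless) have come off. For the parent survey, the same section adds: "The survey will be coded with the study code assigned to the participating infant". It defines no code for staff respondents.

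The Health Care Professional's Survey in Appendix 2 opens with a Subject ID. It then asks for a job category ("Neonatologist () Neonatal Fellow () Pediatric Resident" and further roles) and for experience: "Years of experience: () < 2 years () 2-5 years () 6-10 years () > 10 years". These are the only respondent fields.

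On the route, section 3.3.4 (REDCAP) states: "The HCP and parents will be provided a link to the survey in REDCAP or a hard copy depending on their preference". No respondent log-in or linkage is described.

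The planned use is Aim 1d in section 2.2: "Descriptive analysis of user surveys and their satisfaction with the wireless system". Section 5.1 also puts the staff responses into the interim safety evaluations after 200 and 400 infants, which cover "skin lesion, pain scores, and HCPs survey responses". Section 4 sets the scale: "The proposed sample size is 100 newborns/site (n=600) to be recruited over 2 years". It gives no unit of analysis for the survey and no rule for repeat respondents.

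**The concern.** The request follows the infant, but the answers belong to the staff member. The form asks about satisfaction with wired monitoring, confidence, attitude to the wireless sensors, level of concern and expected impact. Even the item on problems seen (item 5) asks about healthy babies in general, not the infant just monitored. A second form from the same person therefore mostly repeats the first.

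If forms are simply pooled, each person's opinion counts in proportion to how many study infants they attended. A problem that one person saw once could also be ticked again on each later form. The result is a percentage of forms that will be read as a percentage of staff, with no record of how many people stand behind it. This matters even for a purely descriptive analysis, because the weighting changes the percentage itself as well as its precision.

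**Working it through.** The plan states no sample size or precision for the staff survey, so there is no figure to reproduce.

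**Inputs from the documents.** 100 infants per site, 600 in total, over 2 years (section 4). Night and weekend deliveries are expected to be missed because the research team is unavailable (section 3.3.2.1), which narrows the set of shifts that supply respondents.

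**Inputs not in the documents, assumed.** Staff pool per site (S), staff surveyed per infant, and within-person correlation of answers (ICC).

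**1. Are repeats likely?** With one form per infant, a site needs at least 100 different respondents to avoid any repeat. If attendance is random, the expected number of distinct people in 100 forms is S × (1 − (1 − 1/S)^100):

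- S = 20: 19.9
- S = 50: 43.4
- S = 100: 63.4
- S = 200: 78.8
- S = 500: 90.7

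Some repetition is close to certain at any of these pool sizes. How much there is depends on S.

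**2. Effect on the percentage (illustration).** Suppose 4 of 20 staff file half the forms and 90% of them are satisfied, against 50% of the other 16.

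- Per form: 0.5 × 0.9 + 0.5 × 0.5 = 70%
- Per person: 0.2 × 0.9 + 0.8 × 0.5 = 58%

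**3. Effect on the information content (illustration).** Take one form per infant, 600 forms, J staff in all and m = 600/J forms each. The design effect is DE = 1 + (m − 1) × ICC, the effective number is 600/DE, and the 95% half-width at 50% is 1.96 × √(0.25/effective number). The naive half-width with 600 is 4.0 points.

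| J | m | ICC | DE | Effective number | Half-width (points) |
|---|---|---|---|---|---|
| 60 | 10 | 0.3 | 3.7 | 162 | 7.7 |
| 60 | 10 | 0.5 | 5.5 | 109 | 9.4 |
| 60 | 10 | 0.8 | 8.2 | 73 | 11.5 |
| 150 | 4 | 0.3 | 1.9 | 316 | 5.5 |
| 150 | 4 | 0.5 | 2.5 | 240 | 6.3 |
| 150 | 4 | 0.8 | 3.4 | 176 | 7.4 |

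**4. How far the range stretches.** With 100 staff per site and forms spread exactly evenly, m = 1 and DE = 1.0. At the other end, three staff per infant and 10 staff per site give m = 30, and at ICC 0.8 DE = 1 + 29 × 0.8 = 24.2. The assumed inputs therefore decide the size; the documents do not.

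**5. Can it be repaired afterwards?** Role, experience band and site do not identify a person, and the experience band can change over 2 years. The form's field for the person who placed the monitors (Appendix 1, Monitoring Information) belongs to the infant's record and is not tied to whoever answered the survey. De-duplication and per-person weighting are therefore not possible from the listed fields.

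**The case against.** The strongest reply is that section 3.3.4 never says that a staff member must answer again for each infant. The general wording of the items would suit a once-only questionnaire, and infant coding is stated only for parents. That is fair: a reader might infer a deliberate decision to survey the same people after every infant, and the documents do not show one. But the trigger is care of the infant, the form is headed Subject ID, and no once-only rule is written. Sites following the text could collect repeats, and different sites could follow different rules.

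A second reply is that recruitment is slow and the sites are large. One hundred infants in 2 years is about one a week (100/104 weeks), and section 3.3.2.1 lists 2,200 to 11,128 deliveries per site. This bears on how often a person recurs, and it is why the design effect could be near 1. It does not remove the gap, since even a pool of 100 staff gives about 63 distinct people in 100 forms under random attendance.

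Third, a reader might infer that confidence intervals on the survey will be too narrow. No interval or test on the survey is planned, so that is a risk only if one is added later.

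Fourth, a reader might infer that nothing at all could be done afterwards. That is too strong. Patient codes carry a site prefix, so if the Subject ID is the infant's code, site-clustered intervals could allow roughly for the dependence. With six sites they would be crude (t on 5 degrees of freedom, 2.57), and they would not fix the weighting.

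Finally, the interim evaluations attach no survey threshold to any decision, and adverse events are recorded separately. The plan does not support a claim that safety oversight is compromised.

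**Conclusion.** The point holds as a gap in data capture that should be closed before forms are collected. As written, the plan allows the same staff member to be counted repeatedly on standing opinions, over-weights frequent attenders in the Aim 1d percentages and in the staff responses reviewed at 200 and 400 infants, and leaves no means of correcting this at person level.

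Its size cannot be read from the documents. The design effect of 1.9 to 8.2 (about 73 to 316 effective responses out of 600) is an illustration. It rests on one form per infant, 60 to 150 staff sharing the forms evenly, and an ICC of 0.3 to 0.8. It should not be quoted as an estimate for this study.

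The consequence is confined to how the staff percentages are read. Accuracy, coverage, skin and pain results are unaffected.

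**What to change.** - Add an anonymous, persistent respondent code (site plus serial number) to the staff form, the same on paper and through the REDCap link.
- Collect the opinion items once per staff member, or at fixed points such as the first and one set later infant attended. State the rule in section 3.3.4.
- In section 4, name the staff member as the unit for the opinion items, and report the number of distinct respondents alongside the number of forms, including at the 200 and 400 reviews.
- The current form has no infant-specific item. If one is wanted, for example problems seen, reword it to refer to that infant and analyse it with respondent as the cluster.

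The cost is a small change to the form and to REDCap, the wording of any per-infant item, and notifying the ethics boards of a coded, non-identifying number. Asking opinions once also reduces the burden on staff.

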3.3.5 Confidentiality and Protection of Personal Health Information

Participant's personal health information and medical information collected for the purposes of this study will be de-identified or anonymized. Participants will be identified with a unique participant Study code to ensure confidentiality. The key to the unique participant Study code will be kept in a secure file under the supervision of the Principal Investigator (hard copy) and password protected under the Principal Investigator control (electronic copy). All de-identified signal recording data, including annotations, recorded via the BioDash application will be transferred to the secure Dropbox™ professional account. Each member of the research team will be granted access to the Dropbox through their own account with individually assigned login and passwords. Additionally, this data will be uploaded to a hard drive which will be kept in a locked office cabinet to which only members of the research team will have access to.

Information collected via the paper data collection form and paper survey will be transcribed and uploaded to both the secure Dropbox™ professional account as well as Research Electronic Data Capture (RedCap) system. Skin photographs will be edited to remove identifying information (eyes, face, identifying medical tags) and then uploaded to both the secure Dropbox and RedCap data storing systems.

Each participating site will only provide de-identified data in the same manner as described in the protocol and approved by their local regulatory authorities and institutions. Any local requirements will be addressed within the individual site protocols, consents and site agreements. All applicable laws, regulations and guidelines related to data collection, storage, confidentiality, transfer and use will be adhered to as required.

As part of the Smart Hospital Project, this Study and potential future research studies to improve the quality, accuracy and efficiency of monitoring neonates admitted in the NICU, the participants' information may be shared with academic or commercial third parties and used by the research team in other related research studies. Any use of the RI-MUHC and participating site's data in future research studies will be approved by competent research ethics boards and no data that could identify the participant will be shared. Participants at all participating sites will be asked to consent to the sharing of their data collected during this study as well as for use in future research in the field of neonatal care and monitoring. The participants' data will be kept confidential to the extent required by applicable laws. The research agreements with the participating sites will include all the terms and conditions required for the use and sharing of the data from participating sites.

4 Statistical Analysis and Rationale

Sample size: The proposed sample size is 100 newborns/site (n=600) to be recruited over 2 years from start of the Study at each site.

The expected mean and standard deviation are required for estimating the mean effects which is used to determine the absolute precision. In our first study with wireless sensors (see preliminary data) or *phase 1a*, 100 patient recordings (25 infants x 4 days) were expected but only 96 were obtained, resulting in a 4% drop-out rate. Further, the average coverage across wired HR signals was $98.7 \pm 2.2\%$, while that of wireless signals was $85.3 \pm 14.3\%$. Assuming a two-sided significance of 0.05, a study power of 0.9, and accounting for the drop-out rate of 0.04 in all calculations, we can expect an effect size of 2.7% in HR coverage, with the selected sample size of 600 infants. In the case of SpO₂ monitoring, the average coverage was $93.9 \pm 6.3\%$ in the wired system and $66.5 \pm 20.8\%$ in the wireless. In our proposed study, we

can thus expect a difference of 3.46% in SpO₂ coverage. For the statistical measures used to assess the agreement between the wired and wireless vital signals, the average findings from *phase 1a* are reported in the Table. Using the same parameters listed previously, the margin of error expected for each statistical measure in the proposed study can be found.

Statistical measure		Correlation coefficient, C	Proportionality constant, k	Variance accounted for (VAF)	Mean difference (bias), d
Average result in phase 1a	Heart rate (HR)	0.96 ± 0.03	1.00 ± 0.00	91.5 ± 6.5%	0.04 ± 0.32 bpm
	Oxygen saturation (SpO ₂)	0.53 ± 0.23	1.01 ± 0.01	18.9 ± 20.8%	1.43 ± 1.4%
Expected margin of error	Heart rate (HR)	0.01	0.00	1.24%	0.06 bpm
	Oxygen saturation (SpO ₂)	0.04	0.00	3.97%	0.26%

Statistical analytical approach: Descriptive analyses will first be applied to the demographic data. Accuracy analysis of the wireless system to capture the vital signs will be done by using a statistical measure of the strength of a linear relationship between the two systems (correlation coefficient), a measurement of the steepness of this correlation (slope), the ratio of explained and target variance (variance accounted for), and a Bland-Altman plot analysis to evaluate *bias* between the mean differences and estimate an agreement interval.

Each participating site has the facilities and capacity to provide the estimated number of infants to establish feasibility, safety, and accuracy of the device. The wireless device sensors and system being used in the study is approved by Health Canada for research on neonates. Each site will obtain approval from their local and country specific health authorities, as required.

5 Ethical, Legal and Regulatory Considerations

